Appendix J New York Heart Association Functional Classification

Class	Patient Symptoms	Class	Objective Assessment
I	No limitation of physical activity. Ordinary physical activity does not cause undue fatigue, palpitation, dyspnea (shortness of breath).	A	No objective evidence of cardiovascular disease. No symptoms and no limitation in ordinary physical activity.
II	Slight limitation of physical activity. Comfortable at rest. Ordinary physical activity results in fatigue, palpitation, dyspnea (shortness of breath).	B	Objective evidence of minimal cardiovascular disease. Mild symptoms and slight limitation during ordinary activity. Comfortable at rest.
III	Marked limitation of physical activity. Comfortable at rest. Less than ordinary activity causes fatigue, palpitation, or dyspnea.	C	Objective evidence of moderately severe cardiovascular disease. Marked limitation in activity due to symptoms, even during less-than-ordinary activity. Comfortable only at rest.
IV	Unable to carry on any physical activity without discomfort. Symptoms of heart failure at rest. If any physical activity is undertaken, discomfort increases.	D	Objective evidence of severe cardiovascular disease. Severe limitations. Experiences symptoms even while at rest.

Source: <https://www.heart.org/en/health-topics/heart-failure/what-is-heart-failure/classes-of-heart-failure> adapted from Dolgin M, Association NYH, Fox AC, Gorlin R, Levin RI, New York Heart Association. Criteria Committee. Nomenclature and criteria for diagnosis of diseases of the heart and great vessels. 9th ed. Boston, MA: Lippincott Williams and Wilkins; March 1, 1994.

Appendix K Response Evaluation Criteria for Non-Hodgkin Lymphoma

Disease response assessment will be evaluated using the revised Lugano 2014 Classification for NHL ([Cheson et al 2014](#)).

Response assessments will be done by the Investigators following the revised Lugano 2014 Classification response criteria ([Cheson et al 2014](#)).

Tumour assessment will be made for target lesions (ie, measurable disease), non-target lesions (ie, non-measurable disease), organ enlargement (eg, spleen, liver), and new lesions on CT and combined with visual assessment of PET-CT for response assessment ([Cheson et al 2014](#); [Table K35](#)).

K 1 Visual Interpretation of PET-CT Scans

Variation in FDG uptake in a nodal or extranodal sites indicative for lymphoma will be visually assessed using the Deauville 5-point scale.

Target Lesions

Up to a maximum of 6 dominant, measurable lymph nodal or extranodal lesions should be assessed as target lesions and documented at baseline and throughout the study.

A lesion will be considered measurable if:

- For nodal lesions: $LDi > 1.5$ cm
- For extranodal lesion: $LDi > 1$ cm

Lesions visible on PET but not on CT/MRI to be assigned as non-target lesions.

Target nodal or extranodal lesions nodes should be selected according to all of the following:

- They should be clearly measurable in at least 2 perpendicular dimensions
- If possible, they should be from disparate regions of the body
- They should include mediastinal and retroperitoneal areas of disease whenever these sites are involved

The perpendicular long and short axis diameters will be measured and recorded in the transverse plane at baseline and follow-up.

For the selected target lymph nodal lesions, the sum of the product of the perpendicular diameters will be calculated with the percentage change from baseline for assessment of response and nadir for assessment of progression.

Non-target Lesions

All other lesions (including nodal, extranodal, and assessable disease) not selected as target lesions, as well as truly non-measurable sites of disease should be followed as non-measurable disease (eg, cutaneous, gastrointestinal, bone, spleen, liver, kidneys, pleural or pericardial effusions, ascites) and should be factored into the overall response assessment. Non-target lesions will be documented at baseline and throughout the study. Measurement of these lesions is not required to be documented on the eCRFs.

Spleen Involvement

Spleen will be considered to be normal if size of its vertical length (cranial-caudal measurement) is ≤ 13 cm. For patients with splenomegaly at baseline, spleen vertical length will be assessed at screening and all subsequent response evaluations.

Liver Involvement

Intrahepatic lesions should be considered as target, non-target, or new lesion as applicable. The presence of a diffuse or focal uptake with or without focal or disseminated nodules support liver involvement. Given variability in body habitus and the impact of numerous medical conditions, liver size by physical examination or CT scan is not a reliable measure of hepatic involvement by lymphoma. For these reasons, liver size will not be collected in eCRFs.

Bone Marrow Involvement

Bone marrow involvement by lymphoma documented by aspirate and/or biopsy will be reported on the eCRF as present or absent.

Table K35 Response Assessment Criteria for Non-Hodgkin Lymphoma

Response and site	PET-CT-based response	CT-based response
Complete response:	Complete metabolic response:	Complete radiologic response – all of the following:
Lymph nodes and extralymphatic sites (target lesions)	Score 1, 2, or 3 ^a with or without a residual mass on 5PS ^b	Target nodes/nodal masses must regress to ≤ 1.5 cm in LD _i . No extralymphatic sites of disease (0 \times 0 cm)
Non-measured lesion (non-target)	Not applicable	Absent/normal
Organ enlargement	Not applicable	Regress to normal; spleen vertical length is ≤ 13 cm
New lesions	None	None
Bone marrow	No evidence of FDG-avid disease in marrow	Normal by morphology; if indeterminate, IHC negative

Table K35 Response Assessment Criteria for Non-Hodgkin Lymphoma

Response and site	PET-CT-based response	CT-based response
Partial response:	Partial metabolic response:	Partial remission – all of the following:
Lymph nodes and extralymphatic sites	Score 4 or 5 ^b with or without a residual mass on 5PS	≥ 50% decrease in SPD of up to 6 target measurable nodes and extranodal sites
Non-measured lesion	Not applicable	Absent/normal, regressed, but no increase
Organ enlargement	Not applicable	Spleen must have regressed by > 50% in length beyond normal
New lesions	None	None
Bone marrow	Residual uptake higher than uptake in normal marrow but reduced compared with baseline (diffuse uptake compatible with reactive changes from chemotherapy allowed). If there are persistent focal changes in the marrow in the context of a nodal response, consideration should be given to further evaluation with MRI or biopsy or an interval scan	Not applicable
No response or stable disease:	No metabolic response:	Stable disease:
Target nodes/nodal masses, extranodal lesions	Score 4 or 5 with no significant change in FDG uptake from baseline at interim or end of treatment	< 50% decrease from baseline in SPD of up to 6 dominant, measurable nodes and extranodal sites; no criteria for progressive disease are met
Non-measured lesions	Not applicable	No increase consistent with progression
Organ enlargement	Not applicable	No increase consistent with progression
New lesions	None	None
Bone marrow	No change from baseline	Not applicable

Table K35 Response Assessment Criteria for Non-Hodgkin Lymphoma

Response and site	PET-CT-based response	CT-based response
Progressive disease:	Progressive metabolic disease:	Progressive disease requiring at least 1 of the following:
Individual target nodes/nodal masses	Score 4 or 5 with an increase in intensity of uptake from visually determined nadir and/or	
PPD progression:
 
An individual node/lesion must be abnormal with:
 
 • LDi > 1.5 cm AND • Increase by \geq 50% from PPD nadir AND • An increase in LDi or SDi from nadir 
 ◦ 0.5 cm for lesions \leq 2 cm ◦ 1.0 cm for lesions $>$ 2 cm 
In the setting of splenomegaly, the splenic length must increase by $>$ 50% of the extent of its prior increase beyond baseline (eg, a 15 cm spleen must increase to $>$ 16 cm). If no prior splenomegaly, must increase by at least 2 cm from baseline

Non-measured lesions	None	New or clear progression of pre-existing non-measured lesions
New lesions	New FDG-avid foci consistent with lymphoma rather than another aetiology (eg, infection, inflammation). If uncertain regarding aetiology of new lesions, biopsy or interval scan may be considered	
 • Regrowth of previously resolved lesions • A new node $>$ 1.5 cm in any axis A new extranodal site $>$ 1.0 cm in any axis; if $<$ 1.0 cm in any axis, its presence must be unequivocal and must be attributable to lymphoma • Assessable disease of any size unequivocally attributable to lymphoma
Bone marrow	New or recurrent FDG-avid foci	New or recurrent involvement

^a A score of 3 in many patients indicates a good prognosis with standard treatment, especially if at the time of an interim scan. However, in studies involving PET where de-escalation is investigated, it may be preferable to consider a score of 3 as inadequate response (to avoid under treatment). Measured dominant lesions: Up to 6 of the largest dominant nodes, nodal masses, and extranodal lesions selected to be clearly measurable in 2 diameters. Nodes should preferably be from disparate regions of the body and should include, where applicable, mediastinal and retroperitoneal areas. Non-nodal lesions include those in solid organs (eg, liver spleen, kidneys, and lungs), GI involvement, cutaneous lesions, or those noted on palpation. Non-measured lesions: Any disease not selected as measured, dominant disease and truly assessable disease should be considered not measured. These sites include any nodes, nodal masses, and extranodal sites not selected as dominant or measurable or that do not meet the requirements for measurability but are still considered abnormal, as well as truly assessable disease, which is any site of suspected disease that would be difficult to follow quantitatively with measurement, including pleural effusions, ascites, bone lesions, leptomeningeal disease, abdominal masses, and other lesions that cannot be confirmed and followed by imaging. In Waldeyer's ring or in extranodal sites (eg, GI tract, liver, bone

Table K35 Response Assessment Criteria for Non-Hodgkin Lymphoma

Response and site	PET-CT-based response	CT-based response
-------------------	-----------------------	-------------------

marrow), FDG uptake may be greater than in the mediastinum with complete metabolic response, but should be no higher than surrounding normal physiologic uptake (eg, with marrow activation as a result of chemotherapy or myeloid growth factors).

^b PET 5PS: 1, no uptake above background; 2, uptake \leq mediastinum; 3, uptake $>$ mediastinum but \leq liver; 4, uptake moderately $>$ liver; 5, uptake markedly higher than liver and/or new lesions; X, new areas of uptake unlikely to be related to lymphoma.

Adapted from Table 3: Cheson et al 2014

5PS = Deauville 5-point scale; CT = computed tomography; FDG = fluorodeoxyglucose; GI = gastrointestinal; IHC = immunohistochemistry; LDi = longest transverse diameter of a lesion; MRI = magnetic resonance imaging; PET = positron emission tomography; PPD = cross product of the LDi and perpendicular diameter; SDi = shortest axis perpendicular to the LDi; SPD = sum of the product of the perpendicular diameters for multiple lesions.

K 2 Assessment of New Lesions

Appearance of any new lesions > 1.5 cm in any axis during or at the end of therapy, even if all other lesions are decreasing should be considered progression. Increased FDG uptake in a previously unaffected site should only be considered progression after confirmation with other modalities (eg, CT, MRI, biopsy).

In patients with no history of pulmonary lymphoma, new nodules identified by CT are benign and should be considered negative for lymphoma. These lesions typically represent infectious or inflammatory lesions; therefore, if FDG positive, should not be considered positive for lymphoma in the absence of confirmatory tests, (eg, histology).

The presence or absence of new lesions will be recorded in the eCRF.

K 3 Overall Response Assessment

The efficacy endpoints are based on the overall response assessment, which is combining the radiological response from PET/CT scans, the bone marrow findings (if applicable) and any additional clinical finding, including cytologic or histopathologic findings for each disease response assessment during the study. The possible outcomes for ORR as CR, PR, SD, PD, Unknown. The Investigator-assessed ORR and respective date will be captured on the eCRF.

K 4 References

Cheson et al 2014

Appendix L Changes Related to Mitigation of Study Disruptions Due to Cases of Civil Crisis, Natural Disaster, or Public Health Crisis

Note: Changes below should be implemented only during study disruptions due to any of or a combination of civil crisis, natural disaster, or public health crisis (eg, during quarantines and resulting site closures, regional travel restrictions and considerations if site personnel or study patients become infected with SARS-CoV-2 or similar pandemic infection) during which patients may not wish to or may be unable to visit the study site for study visits. These changes should only be implemented if allowable by local/regional guidelines and following notification from the Sponsor and instructions on how to perform these procedures will be provided at the time of implementation.

Please note that during civil crisis, natural disaster, or public health crisis, some study assessments and procedures may not be conducted due to international or local policies or guidelines, hospital or clinic restrictions and other measures implemented to ensure the patient's safety. If in doubt, please contact the Study Physician.

L 1 Reconsent of Study Patients During Study Interruptions

During study interruptions, it may not be possible for the patients to complete study visits and assessments on-site and alternative means for carrying out the visits and assessments may be necessary, eg, remote visits. Reconsent should be obtained for the alternative means of carrying out visits and assessments and should be obtained prior to performing the procedures described in Sections [L 2](#) to [L 5](#). Local and regional regulations and/or guidelines regarding reconsent of study patients should be checked and followed. Reconsent may be verbal if allowed by local and regional guidelines (note, in the case of verbal reconsent the ICF should be signed at the patients' next contact with the study site). Visiting the study sites for the sole purpose of obtaining reconsent should be avoided.

L 2 Rescreening of Patients to Reconfirm Study Eligibility

Additional rescreening for screen failure due to study disruption can be performed in previously screened patients. The Investigator should confirm this with the designated Study Physician.

In addition, during study disruption there may be a delay between confirming eligibility of a patient and either enrolment into the study or commencing of dosing with study intervention. If this delay is outside the screening window specified in the SoA of the respective modules, the patient will need to be rescreened to reconfirm eligibility before commencing study procedures. This will provide another opportunity to rescreen a patient in addition to that detailed in Section [5.4](#).

L 3 Home or Remote Visit to Replace On-site Visit (where applicable)

A qualified HCP from the study site or TPV service may visit the patient's home/or other remote location as per local standard operating procedures, as applicable. Supplies will be provided for a safe and efficient visit. The qualified HCP will be expected to collect information per the CSP.

L 4 Telemedicine Visit to Replace On-site Visit (where applicable)

In this appendix the term telemedicine visit refers to remote contact with the patients using telecommunications technology including phone calls, virtual or video visits, and mobile health devices.

During a civil crisis, natural disaster, or public health crisis, on-site visits may be replaced by a telemedicine visit if allowed by local/regional guidelines. Having a telemedicine contact with the patients will allow AEs, concomitant medication, and ECOG performance status to be reported and documented.

L 5 Data Capture During Telemedicine or Home/Remote Visits

Data collected during telemedicine or home/remote visits will be captured by the qualified HCP from the study site or TPV service in the source documents, or by the patient themselves.

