5.1 Inclusion Criteria

Patients are eligible to be included in the study only if all of the core criteria below and all criteria from the relevant individual modules apply. Where specific module criteria differ from core inclusion criteria, the most stringent criteria should be applied.

Informed Consent

- 1 Provision of signed and dated written informed consent, as described in [Appendix A](#), prior to any study-specific procedures, sampling, and analyses. Informed consent includes compliance with the requirements and restrictions listed in the ICF and in this CSP.

Age

- 2 Patient must be aged \geq 18 years at the time of signing the informed consent. In some countries, parental consent may be required in addition to an assent form for patients who are 18 years of age.

Type of Patient and Disease Characteristics

- 3 Patient must have histologically documented diagnosis of B-NHL as defined by a B-cell neoplasm in the World Health Organisation classification scheme except as noted in the exclusion criteria.
- 4 Patient has relapsed after or failed to respond to at least 2 but no more than 5 prior systemic treatment regimens (including investigational therapy) and for whom there is no available therapy expected to improve survival (eg, standard chemotherapy, autologous SCT, CAR-T cell therapy).
- 5 Documented active disease requiring treatment that is relapsed or refractory defined as:
 - Recurrence/relapse of disease after response to prior line(s) of therapy.
 - Progressive disease (refractory) on/after completion of the treatment regimen preceding entry into the study.
- 6 Must have at least one measurable FDG-PET avid lesion (except for MZL), based on bi-dimensional assessment on PET and CT/MRI scan. A measurable lesion is defined as:
 - For nodal lesions: longest diameter > 1.5 cm
 - For extranodal lesions: longest diameter > 1 cm
- 7 ECOG performance status score ≤ 2 . Performance status must not have deteriorated by ≥ 2 levels within 2 weeks after providing informed consent.
- 8 Adequate haematologic, hepatic, and renal function as defined in [Table 3](#).

Table 3 Criteria for Adequate Organ and Marrow Function

Parameter	Criteria	
Haematologic	Haemoglobin	$\geq 8.0 \text{ g/dL (5.59 mmol/L)}$ with no whole blood transfusions within 14 days prior first dose of AZD0466

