10.5.1.2 Additional Inclusion Criteria for Cohort B2 (R/R FL or MZL)

- 1 Histologically confirmed diagnosis of FL Grade 1, 2, or 3a OR histologically confirmed MZL including splenic, nodal, and extranodal subtypes, as assessed by Investigator or local pathologist with documented active disease requiring systemic treatment.
- 2 For FL patients: Previously received at least 2 prior systemic treatment regimens (including anti-CD20 mAb and an alkylating agent).
- 3 For MZL patients: Previously received at least 2 prior lines of systemic therapy including at least one anti-CD20 mAb-directed regimen either as monotherapy or as chemoimmunotherapy (*Helicobacter pylori* eradication and radiation therapy alone will not be considered a systemic treatment regimen).

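### Appendix K 1 and Table K35 disagree on which target lesions enter the CT sum and on how progression is measured, and nothing says which governs

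*Protocol*

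**What the plan says.** Protocol Appendix K 1 (Target Lesions) opens the choice of targets to both kinds of disease: "Up to a maximum of 6 dominant, measurable lymph nodal or extranodal lesions should be assessed as target lesions". The calculation that follows is narrower: "For the selected target lymph nodal lesions, the sum of the product of the perpendicular diameters will be calculated with the percentage change from baseline". The sentence continues "for assessment of response and nadir for assessment of progression". K 1 attaches no percentage to either use.

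Table K35, in the same appendix, assigns the CT categories:

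- **PR:** at least a 50% "decrease in SPD of up to 6 target measurable nodes and extranodal sites".
- **SD:** less than a 50% "decrease from baseline in SPD of up to 6 dominant, measurable nodes and extranodal sites; no criteria for progressive disease are met".
- **PD of measured lesions:** "An individual node/lesion must be abnormal with" a longest diameter (LDi) above 1.5 cm, a product of diameters (PPD) at least 50% above its nadir, and a rise in LDi or the short axis of 0.5 cm (lesions up to 2 cm) or 1.0 cm (larger lesions). The table has no PD criterion based on the change of the sum (SPD) from nadir.

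One extranodal lesion is enough for the measurable-disease criterion in Protocol Section 5.1: "For extranodal lesions: longest diameter > 1 cm". Cohort B2 admits "histologically confirmed MZL including splenic, nodal, and extranodal subtypes" (Section 10.5.1.2). The investigator's overall response serves the primary and secondary endpoints (Protocol Section 8.1.3.1). SAP Section 5.2.1.1 takes best response from the investigator's visit responses and does not re-derive it from lesion measurements.

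**The concern.** K 1 tells the investigator how to form the sum, and Table K35 tells the investigator how to read it, but the two sums are not the same quantity. Two sites could classify the same CT measurements differently. So could a site and a later central reader, since Protocol Section 8.1.2 leaves central review open.

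One visit can matter. SAP Section 5.2.1.1 does not require a response to be confirmed, so a single PR or SD call can decide whether a patient counts in ORR. TTR runs to the first response. DoR ends on the PFS event (SAP Section 5.2.3.2), so a missed or late progression moves both DoR and PFS. Response also informs the Part B interim analysis (Protocol Sections 10.9.2 and 10.9.5).

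CT carries most weight where PET is absent. Section 8.1.2 schedules CT without PET at Weeks 16 and 36 and lets patients with confirmed CR be followed by CT alone. A footnote to Table 13 asks only for CT in MZL with non-avid lesions.

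**Working it through.** The plan gives no figure to reproduce, because this is a classification rule. The thresholds below are those of Table K35. The lesion measurements (cm) are illustrative assumptions. New lesions, non-target disease, spleen, marrow and PET are taken as neutral.

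Formulas: PPD = LDi × perpendicular diameter; SPD = sum of PPDs; change = 100 × (new − reference) / reference.

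**Response, change from baseline, with the table's 50% cut-off applied to each sum**

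| Case | Nodal sum (K 1) | All-target sum (Table K35) |
|---|---|---|
| A. Node 3.0×3.0 to 2.0×2.0; extranodal 5.0×4.0 to 5.0×3.8 | 9 to 4: −5/9 = −55.6%, reaches PR | 29 to 23: −6/29 = −20.7%, SD |
| B. Node PPD 9.0 to 8.1; extranodal PPD 20 to 6 | 9 to 8.1: −0.9/9 = −10.0%, SD | 29 to 14.1: −14.9/29 = −51.4%, reaches PR |
| C. One extranodal target, 3×2 to 2×1.4 | No nodal target, percentage undefined | 6 to 2.8: −3.2/6 = −53.3%, reaches PR |

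The category moves in both directions (A, B), and in C the K 1 sum does not exist. This conflict needs at least one extranodal target. With nodal targets only, the two sums are identical.

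**Progression, change from nadir**

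- Case D, nodes only: one node goes from 2×1.5 to 3×2 and another from 4×4 to 3×3. First node: PPD 3 to 6 = +100%, LDi +1.0 cm and now 3 cm, so PD under Table K35. Nodal SPD: 3 + 16 = 19 to 6 + 9 = 15, that is −4/19 = −21.1%.
- Case E: nodes of 3×2 and 2.5×2 are unchanged and an extranodal target goes from 2×1.5 to 3×2. The extranodal lesion has PPD +100% and LDi +1.0 cm, so PD under Table K35. Nodal SPD: 11 to 11, 0%.

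In D and E the K 1 sum does not rise, so no positive cut-off would flag progression. D shows that this half of the conflict does not need extranodal disease.

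- Case F, the reverse direction: four nodes go from 1.6×1.2 to 2.0×1.5. SPD: 4 × 1.92 = 7.68 to 4 × 3.0 = 12.0, that is +56.3%. The largest diameter increase is 0.4 cm, below 0.5 cm, so not PD under Table K35. It would be PD on the K 1 sum only if a 50% cut-off were assumed, and K 1 states none.

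**The case against.** The strongest reply is that K 1 is not a rival set of criteria. It has no cut-offs, so it cannot by itself yield PR, SD or PD. The opening of Appendix K cites Table K35. The protocol names the revised Lugano 2014 classification as its standard, and the table is stated to be adapted from that publication. In the table one PD criterion suffices, and SD requires that none is met. An investigator who follows the table literally reaches one answer in every case above, and a patient with only extranodal targets is pushed to the table because the K 1 sum is empty.

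Much of this stands, and many investigators may work that way. But K 1 is the explicit instruction for calculating the sum, and no sentence places it below the table. Forming the sum as K 1 says and then reading it against the table's 50% is a natural way to use the two together, and it gives the wrong category in cases A and B.

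A reader might infer more than the documents support:

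- *That the CR rate is affected.* CT-based CR in Table K35 rests on node diameter and absence of extralymphatic disease, not on the SPD.
- *That CT is the only imaging possible at Weeks 16 and 36.* It is the only scheduled imaging. Section 8.1.2 permits extra PET-CT when clinically indicated and asks for PET to confirm a new CT-based CR. K 3 also brings in marrow and clinical findings.
- *That the eCRF calculates the nodal sum.* The eCRF is not among the documents, and the SAP describes no SPD derivation.
- *That extranodal-only patients will be common.* Eligibility allows them, but no share is given.
- *That growth from, say, 2.0 to 2.6 cm is plainly PD under the table.* The table does not say whether the 2 cm boundary is read at nadir or at the current scan. Cases D and E do not depend on this.

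**Conclusion.** The inconsistency is real and sits in the rule behind the primary endpoint. It has two parts. First, if the table's 50% cut-off is applied to the K 1 sum, PR and SD can swap in either direction when a target is extranodal, and no sum exists when all targets are. Second, a site that judges progression by the K 1 sum can miss a single-lesion PD, even with nodal targets only.

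The conclusion is conditional on a site following K 1 rather than the table, and it concerns the CT component only. ORR, DoR, TTR and PFS can be affected; the CT definition of CR is not. It would go too far to say that PD will be delayed or ORR biased in a known direction: the examples run both ways and use assumed measurements. The size cannot be estimated, because the Part B cohort sizes are blacked out and the share of patients with extranodal targets is not stated. The correction is still worth making now, because it is cheap and removes a choice that should not be left to sites.

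**What to change.** Reconcile K 1 with Table K35 by replacing the K 1 sentence with: *For all selected target lesions (nodal and extranodal), the SPD and its percentage change from baseline are used for assessment of response; progression is assessed per individual lesion from its own PPD nadir, as in Table K35.* Check any eCRF calculation against that text, and check response calls already made against it.

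The cost is a small protocol amendment, with the ethics and regulatory approval that Appendix A 1 requires. No new scans or measurements are needed, since K 1 already has both diameters of target lesions recorded at baseline and follow-up.

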Coagulation	X	X	X	X	X			8.2.4
Cortisol, ACTH, TSH					X			8.2.4

Table 14 Schedule of Activities for Module 1 Part A and Part B: Cycle 2 and Beyond and Follow-up

Procedures	Cycle 2 (28 days)		Cycle 3 and beyond (28 days)		EoT	Follow-up		Details in CSP section or appendix
	Day	1	8/15/22	1		Post-treatment FU visit (28 days after last dose)	Q3M after post-treatment FU visit	
Visit window	± 2 days				± 7 days			
Troponin I ^a					X			8.2.4
BNP (or NTproBNP)					X			8.2.4
Urinalysis	X	X	X	X	X			8.2.4
Disease assessments								
CT scan	Weeks 8, 16, 24, 36, 48 and thereafter every 24 weeks for R/R FL and MZL, and every 16 weeks for R/R MCL and R/R DLBCL, until disease progression							8.1.2
FDG-PET scan	Week 8, 24 and 48 and thereafter once a year. If confirmed CR, no further PET scans are required.							8.1.2
Bone marrow biopsy/aspirate	To confirm CR (if prior bone marrow involvement) or as clinically indicated							8.1.1
Endoscopy/histology	To confirm CR (if prior gastrointestinal involvement), or as clinically indicated							8.1.4.1
Brain MRI/CT scan	Only if clinically indicated							8.1.2
B-symptoms	To be collected at Screening, and every tumour assessment scan							8.1.4.3
Study intervention								
Administer AZD0466	X	X	X	X				6.1, 10.6.1
Prophylaxis for Tumour Lysis Syndrome								
Prophylaxis for TLS	X ^b (based on risk profile)	X ^b (based on risk profile)	X ^b (based on risk profile)	X ^b (based on risk profile)				Appendix F
Pharmacokinetic assessments								
Blood samples for plasma PK	X ^c		C3D1 ^c , C5D1 ^c					10.8.5.1

Table 14 Schedule of Activities for Module 1 Part A and Part B: Cycle 2 and Beyond and Follow-up

Procedures	Cycle 2 (28 days)		Cycle 3 and beyond (28 days)		EoT	Follow-up		Details in CSP section or appendix	
	Day	1	8/15/22	1		Post-treatment FU visit (28 days after last dose)	Q3M after post-treatment FU visit		
Visit window	\pm 2 days				\pm 7 days				
Exploratory and biomarkers assessments									
Blood samples for CCI	X	D15 (Part B only)	C3D1, C5D1, C7D1, C9D1 (and at every tumour assessment scan)		X			8.1.4.2, 10.8.6.4	
Blood samples for CCI	X	D15 (Part B only)	C3D1, C5D1, C7D1, C9D1 (and at every tumour assessment scan)		X			10.8.6.5	
Blood samples for CCI	X		C3D1, C5D1 (and at every tumour assessment scan during Part B only)		X			10.8.6.6	
Blood samples for CCI	X		C3D1, C5D1 (and at every tumour assessment scan during Part B only)		X			10.8.6.7	

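### Table K35 limits the PET-CT complete response row to target lesions, against its own PR row and K 1 and K 3, so the CR rate can be overstated or scored inconsistently when a non-target lesion stays avid

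*Protocol*

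**What the plan says.** All of this is in Protocol Appendix K unless another place is named.

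- **CR block of Table K35.** The PET-CT requirement of score 1, 2 or 3 is in the row "Lymph nodes and extralymphatic sites (target lesions". The next row, "Non-measured lesion (non-target", is marked not applicable under PET-CT; under CT such lesions must be absent or normal.
- **PR block.** The matching row covers lymph nodes and extralymphatic sites with no restriction to targets, and asks for score 4 or 5.
- **PD block.** The PET rule on rising uptake is in the row "Individual target nodes/nodal masses". The PET cell for non-measured lesions reads none.
- **K 1, which lesions are non-target.** At most 6 lesions are targets, and a node must exceed 1.5 cm to be measurable. Everything else is non-target, with this addition: "Lesions visible on PET but not on CT/MRI to be assigned as non-target lesions".
- **K 1, how they count.** "Variation in FDG uptake in a nodal or extranodal sites indicative for lymphoma will be visually assessed using the Deauville 5-point scale". Non-target disease "should be factored into the overall response assessment", and "Non-target lesions will be documented at baseline and throughout the study".
- **K 3.** The efficacy endpoints rest on an overall response that combines PET/CT, marrow and other clinical findings.
- **PET after CR.** Table 14 (Section 10.1.3) states: "If confirmed CR, no further PET scans are required". Section 8.1.2 asks for a negative PET to confirm a CT-based CR, then allows CT-only follow-up.

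**The concern.** The table is what an investigator will use to assign the visit response, and it gives no PET criterion for non-target disease in the CR block. The lesions most exposed are those that CT cannot judge: lesions seen only on PET, and avid nodes of normal size. K 1 makes both non-target by definition.

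Protocol Section 8.1.3.1 uses the investigator's overall response for the primary and secondary endpoints, and central review is optional (Section 8.1.2). K 1 does not require measurements of non-target lesions on the eCRF. Two investigators reading the same scan differently would therefore be hard to detect or correct later. At stake is mainly the CR rate, which SAP Section 5.2.2.2 reports with exact 80% and 95% intervals.

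**Working it through.** The plan gives no figure to reproduce, so the check is to apply the table row by row and then compare the result with the surrounding text.

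**Test patient (hypothetical).** All targets at score 2 and regressed on CT; one PET-only lesion, present at baseline, still at score 5; no new lesion; spleen normal; marrow not avid and morphologically normal.

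| CR row in Table K35 | PET-CT column | CT column |
|---|---|---|
| Nodal and extralymphatic (targets) | Score 1 to 3: met | Regressed: met |
| Non-measured (non-target) | Not applicable: no test | Absent or normal: met, because CT does not show the lesion |
| Organ enlargement | Not applicable | Met |
| New lesions | None: met | None: met |
| Marrow | Not avid: met | Normal: met |

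Every CR row is satisfied in both columns. An avid non-target node of normal size gives the same result.

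**Same patient, PR block.** The PET-CT row for nodal and extralymphatic sites has no target limit, so a score of 5 at the PET-only lesion fits PR. The table does not say which category prevails.

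**Same patient, K 1 and K 3.** The avid site is scored on the Deauville scale and counts in the overall response, so CR is not supported. K 1 does not say how it counts, and the radiological part of the K 3 combination is what Table K35 defines.

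**PD block.** Suppose uptake in that lesion then rises.
- The PET rule for rising uptake is in a target-only row, so it does not apply.
- The new-foci rule does not apply, because the lesion was there at baseline.
- The CT rule for clear progression of existing non-measured lesions applies only once CT shows the lesion.

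**Effect on each endpoint.**
- *ORR* (SAP 5.2.1.1) counts CR and PR alike, so a CR/PR swap changes nothing. It would move only if the non-target lesion took the overall response to stable or progressive disease.
- *CR rate* (SAP 5.2.2.1): each reclassified patient moves it by 100/n percentage points. Cohort sizes are redacted. For illustration only, n = 20 gives 100/20 = 5.0 points and n = 40 gives 100/40 = 2.5 points.
- *DoR* (SAP 5.2.3.2) starts at the first CR or PR, so a swap does not move its start. The end of DoR, and PFS with it, could move only through later detection of progression. Scheduled PET is at Weeks 8, 24 and 48, then yearly. A CR confirmed at Week 8 removes the requirement for the Week 24 and Week 48 scans, while CT continues on the same schedule. The documents give nothing from which to size this.

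**The case against.** The strongest reply is that the label is a slip and the rest of the appendix makes the intent clear. K 1 does not confine Deauville scoring to targets. Footnote b of Table K35 includes new lesions in score 5, and a new lesion cannot be a target. Footnote a limits residual uptake at extranodal sites in complete metabolic response without mentioning targets. The not-applicable entry for non-measured lesions also appears in the PR and stable disease blocks, where it may mean only that the size-based split has no place on PET. Section 8.1.2 requires a negative PET to confirm a CT-based CR, and a scan with a score 5 lymphoma lesion is not plausibly negative.

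This stands as evidence of intent, and a careful investigator may well reach the intended answer. It does not supply the missing rule. Footnote a covers Waldeyer's ring and extranodal sites, not an avid non-target node. Section 8.1.2 does not define a negative PET, and the PET response criteria on offer are those of Table K35. The supporting text therefore shows that the table conflicts with it; it does not resolve the conflict.

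The reply does rule out several stronger readings that a reader might infer:
- *That non-target disease is not tracked for progression.* It is documented throughout, and new avid foci, new or recurrent marrow foci and clear CT progression of non-measured lesions all count. The gap is rising uptake in an existing non-target lesion, chiefly a PET-only one.
- *That any avid disease beyond the 6 targets slips through.* A non-target lesion still abnormal on CT fails the CT cell, and Appendix K combines CT with PET.

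**Conclusion.** The inconsistency is real and worth correcting. The CR row label and the non-target PET entry conflict with the table's PR row, with K 1 and with K 3. Applied literally, they allow CR and PR at once for a patient with a persisting avid PET-only lesion or avid normal-sized node.

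The supported conclusion is that the investigator-assessed CR rate can be overstated or scored inconsistently. The documents do not show that it is overstated: that depends on how investigators read the table and on how many such patients there are, and neither is known. Nor do they show that DoR and PFS are lengthened. That effect is possible through the PET scans no longer required after confirmed CR, but it is unquantified. ORR, the Part B primary endpoint, is unaffected by a CR/PR swap.

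The total effect on the CR rate cannot be derived. The 5.0 to 2.5 points per patient rest on an assumed 20 to 40 patients per cohort. No formal hypothesis test is planned, so the consequence is a less reliable descriptive estimate, not an error rate.

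**What to change.** 1. In the CR block of Table K35, remove the restriction to target lesions from the PET-CT row, or state that score 1 to 3 is required at every lymphoma site, target and non-target, including PET-only lesions.
2. State the consequence outright: a patient with a non-target lymphoma site at score 4 or 5 is not CR. This removes the overlap with PR.
3. In the PD block, reconcile the target-only row label with K 1, so that the table says how rising uptake in an existing non-target site is handled.
4. Carry the same wording into the eCRF response instructions.

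The cost is wording in Table K35 and the eCRF instructions; the scans are already scheduled. The CR rate may come out slightly lower.
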